10.3. Variables and planned statistical analyses

10.3.1. Primary variables

Efficacy variables

The primary efficacy endpoint is the adjudicated composite of all-cause death, any stroke, myocardial infarction (MI), symptomatic valve thrombosis, pulmonary embolism (PE), deep vein thrombosis (DVT), or non-CNS systemic embolism.

Safety variables

The primary safety endpoint is defined as the adjudicated composite of life-threatening, disabling or major bleeds classified according to the VARC definitions following the BARC classification. This endpoint is referred to as the primary bleeding event (PBE).

10.3.2. Secondary variables

The secondary endpoints are:

- the adjudicated composite of cardiovascular death, any stroke, myocardial infarction, symptomatic valve thrombosis, pulmonary embolism, deep vein thrombosis, or non-CNS systemic embolism
- The net-clinical-benefit defined as the adjudicated composite of all-cause death, any stroke, myocardial infarction, symptomatic valve thrombosis, pulmonary embolism, deep vein thrombosis, non-CNS systemic embolism (efficacy), life-threatening, disabling, and major bleeds (safety).

The secondary safety endpoints are bleeding complications according to:

- The composite of TIMI major or minor bleeds
- ISTH major bleeding
- The composite of BARC 2, 3 or 5 bleeds

10.3.3. Other variables

Other variables include:

- the separate components of the adjudicated primary efficacy and safety endpoint being,
 - All-cause death
 - Any stroke
 - Myocardial infarction
 - Symptomatic valve thrombosis
 - Pulmonary embolism
 - Deep vein thrombosis
 - Non-CNS systemic embolism

- Life-threatening or disabling bleeds (BARC type 3b, 3c or 5)
- Major bleeds (BARC type 3a)
- mean transaortic valve pressure gradient at approximately 360 days after randomization measured by echocardiogram (TTE or TEE)

10.3.4. Subgroup variables

This section was modified with Amendment 3. For details, see Section 15.2.

The following subgroup variables based on baseline demographics are planned according to the subgroup analysis (see 10.3.8):

- Sex (male, female)
- Age (< Median, \geq Median)
- Weight
- BMI
- Valve type (balloon-expandable, self-expandable)
- Valve-in-valve procedure
- Surgical Risk Scores, such as Society of Thoracic Surgeons' (STS) risk score and/or EuroSCORE
- Renal function
- Hypertension (yes, no)
- Diabetes mellitus (yes, no)
- History of a prior stroke (ischemic or unknown type) or non-CNS systemic embolism (yes, no)
- Prior MI (yes, no)
- Previous revascularization (CABG or PCI)
- CHADS₂ and CHA₂DS₂-VASc scores (< Median, \geq Median)
- HAS-BLED (< Median, \geq Median)
- Frailty index

10.3.5. Analysis of the primary efficacy variable

This section was modified with Amendment 3. For details, see Section 15.2.

The analysis of the primary efficacy variable is performed on the Full Analysis Set (FAS). For superiority analysis the follow-up is censored at the last date of known outcome status or at the efficacy cut-off date, whichever comes first. Non-inferiority analysis is carried out under the OT data scope, i.e. follow-up is censored at two days after permanent discontinuation of the randomized treatment strategy. Censoring is assumed independent of the treatment group assignment.

10.3.5.1. Testing for superiority

This section was modified with Amendment 3. For details, see Section 15.2.

In order to evaluate whether the rivaroxaban-based strategy is superior to the antiplatelet-based strategy in prolonging the time to primary efficacy outcome event in patients with post-TAVR patients, the following null hypothesis (H_0) is tested at the significance level of 2.5%:

$H_0: S_{RIV}(t) = S_{APT}(t)$ for all time points $t \geq 0$, (i.e. “there is no difference between the rivaroxaban-based treatment group and the antiplatelet-based control group regarding the primary efficacy outcome for all time points”)

The one-sided alternative hypothesis is:

$H_1: S_{RIV}(t) > S_{APT}(t)$ for at least one time point $t \geq 0$, and $S_{RIV}(t) \geq S_{APT}(t)$ for all time points $t \geq 0$, (i.e. “there is a difference between the two groups in favor of the rivaroxaban-based treatment group regarding the primary efficacy outcome for at least one time point”)

where S_{RIV} denotes the event-free survival function of the rivaroxaban-based treatment group and S_{APT} denotes the event-free survival function of the antiplatelet-based treatment group.

The following decision rule to test the null hypothesis is applied:

According to the size of this study, it is justified to assume under H_0 a sufficiently close approximation of the one-sided log-rank test to the normal distribution. If the z-value from the one-sided log-rank test (for the difference $S_{RIV}(t) - S_{APT}(t)$) is larger than the critical quantile from the normal distribution ($z_{0.975} = 1.96$), the null hypothesis is rejected in favor of the alternative hypothesis.

Kaplan-Meier estimates of cumulative risk and cumulative hazard functions are provided to evaluate the timing of event occurrence in the different treatment groups and the consistency of the respective treatment effects for all time points.

Hazard ratio and corresponding two-sided 95% confidence intervals are estimated based on a Cox proportional hazards models. The parameter estimate β ($=\ln(HR)$), its standard error, p-value, and 95% Confidence Limits are calculated according to the maximum partial likelihood method, with Breslow's approximation for ties (phreg).

The plausibility of proportional hazards assumption will be assessed by visually comparing the plot of the log of cumulative hazard between treatments and by additionally adding a treatment by logarithm-transformed time interaction into the Cox model. If there is strong evidence of non-proportionality, the estimation of time-dependent hazard ratios will be considered.

All of the above analyses are carried out under the ITT data scope (i.e. all events are counted irrespective of the actual treatment at the time of the event).

Further details will be specified in SAP.

10.3.5.2. Testing for non-inferiority

This section was modified with Amendment 3. For details, see Section 15.2.

Using a log rank test adapted to non-inferiority testing the following (inferiority) null hypothesis (H_0) is tested at a one-sided significance level of 2.5%:

H_0 : $HR(t) \geq 1.2$ for all time points $t \geq 0$, (i.e. “the hazard for the primary efficacy endpoint in the rivaroxaban-based treatment group is more than 20% larger than that in the antiplatelet-based control group regarding”)

The one-sided alternative hypothesis (H_1) is:

H_1 : $HR(t) < 1.2$ for all time points $t \geq 0$, (i.e. “the hazard in the rivaroxaban-based treatment group for the primary efficacy endpoint is such that the HR is below 1.20”)

The following decision rule to test the null hypothesis of inferiority is applied:

If the upper boundary of 95% confidence interval (CI) for HR falls below 1.20, the null-hypothesis of inferiority (H_0) is rejected and non-inferiority of the rivaroxaban-based strategy (relative to the antiplatelet-based strategy) with regard to the primary efficacy endpoint can be claimed.

Hazard ratio and corresponding two-sided 95% confidence intervals are estimated based on a Cox proportional hazards model.

In order to preserve the type I error rate for efficacy testing, the two tests for the primary efficacy endpoint are technically placed in a hierarchical order, (1) testing for non-inferiority as described in this section followed by (2) testing for superiority as described in the previous section.

10.3.5.3. Exploratory analyses of the primary efficacy variable

In the primary analyses, switches to full dose anticoagulation are treated as integral part of the treatment strategy. Pre-NOAF analyses, with censoring at the time of the switch to anticoagulation therapy, are carried out as exploratory analyses. Post-NOAF analyses, with starting at the time of the treatment switch precipitated by NOAF are carried out as exploratory analyses.

10.3.6. Analysis of secondary and other efficacy variables

The secondary efficacy and net-benefit variables are tested sequentially in a hierarchical order as listed in Section 10.3.2.

If the superiority of rivaroxaban-based strategy for the primary efficacy outcome is declared, the following alternative hypotheses, superiority of rivaroxaban-based strategy compared with antiplatelet-based strategy for the secondary efficacy endpoints is tested in the sequential order. If an individual test during any step is not statistically significant, further testing may continue but significance will not be claimed. This hierarchical testing procedure controls the global Type 1 error level.

The analysis methods are similar to those described for the primary efficacy variable. The analyses are carried out under the ITT data scope. In these analyses, testing for superiority is not preceded by testing for non-inferiority.

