5.2 Data scopes

5.2.1 Data scopes according to intention-to-treat principle (ITT analysis)

Efficacy cut-off date

When the anticipated efficacy cut-off date is set, the sponsor informs each investigational site and all subjects must return to the clinic within 6 weeks in order to have a final assessment. This assessment will coincide with the EOT visit for the subjects under treatment. The efficacy cut-off date is the date when the study treatments are discontinued. This date will be determined by the Executive Committee (see protocol 5.3.3). From this day onwards subjects will be transitioned from the assigned strategy to an appropriate therapy, as per the clinical site standard of care.

Censoring of follow-up in ITT analysis

Censoring of follow-up for patients is on the efficacy cut-off date, or date of last known clinical status collected from Last Clinical Status form, or date of death (by CEC adjudication) whichever comes first.

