6.2 Efficacy

The primary efficacy endpoint is death or first adjudicated thromboembolic event (DTE), defined as the adjudicated composite of

- All-cause death
- Any stroke
- Myocardial infarction (MI)
- Symptomatic valve thrombosis
- Pulmonary embolism (PE)
- Deep vein thrombosis (DVT)
- Non-central nervous system (CNS) systemic embolism

The endpoint definitions are located in sections 16.1 and 16.2 of the protocol.

The secondary efficacy endpoints, analyzed hierarchically, are

- The adjudicated composite of cardiovascular death (including unknown of unexplained death), any stroke, myocardial infarction, symptomatic valve thrombosis, pulmonary embolism, deep vein thrombosis, or non-CNS systemic embolism
- The net-clinical-benefit defined as the adjudicated composite of all-cause death, any stroke, myocardial infarction, symptomatic valve thrombosis, pulmonary embolism, deep vein thrombosis, non-CNS systemic embolism (efficacy); life-threatening, disabling and major bleeds (safety).

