6.2.1.2 Testing for superiority

If, for the primary efficacy endpoint (DTE), non-inferiority of the rivaroxaban-based strategy can be claimed, superiority of the rivaroxaban-based strategy for the primary efficacy endpoint (DTE) is tested with the following hypothesis (H_0) at the significance level of 2.5%

$H_0: S_{RIV}(t) = S_{APT}(t)$ for all time points $t \geq 0$, (i.e. “there is no difference between the rivaroxaban-based treatment group and the antiplatelet-based control group regarding the primary efficacy endpoint at all time points”)

The one-sided alternative hypothesis (H_1) is:

$H_1: S_{RIV}(t) > S_{APT}(t)$ for at least one time point $t \geq 0$, and $S_{RIV}(t) \geq S_{APT}(t)$ for all time points ≥ 0 (i.e. “there is difference between the two groups in favor of the rivaroxaban-based treatment group for the primary efficacy endpoint at all time points”)

where S_{RIV} denotes the event-free survival function of the rivaroxaban-based treatment group and S_{APT} denotes the event-free survival function of the antiplatelet-based treatment group.

The following decision rule to test the null hypothesis is applied:

According to the size of this study, it is justified to assume under H_0 a sufficiently close approximation of the one-sided log-rank test to the normal distribution. If the z value from the one-sided log-rank test (for the difference $S_{RIV}(t) - S_{APT}(t)$) is larger than the critical quantile from the normal distribution ($z_{0.975} = 1.96$), the null hypothesis is rejected in favor of the alternative hypothesis.

Kaplan-Meier curves, one-sided log rank p-value, number of patients with event and incidence rate are provided to evaluate the timing of event occurrence in the different treatment groups and the consistency of the respective treatment effects for all time points.

The following SAS code may be used:

```
proc lifetest data=work.infile  notable;
  time d2fDTE*DTE(0);
  strata treat /test=(logrank);
run;
/*
where
work.infile = name of source dataset
treat       = randomization code
DTE         = death and thromboembolic event
d2fDTE     = days to first DTE (since randomization)
*/

```

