6.5 Other analysis

Pre-NOAF and post-NOAF analysis are carried out as an exploratory analysis for the primary efficacy variable (DTE). On treatment, pre-NOAF and post-NOAF analysis are carried out as an exploratory analysis for the primary safety (PBE) variable. The analyses are done analogue to the superiority HR analysis as described in [6.2.1.2](#) and are visualized in [flowchart 4](#).

The separate components of the adjudicated primary efficacy and safety endpoint are analyzed exploratory and analogue to the superiority HR analysis as described in [6.2.1.2](#). The separate components of the adjudicated primary efficacy and safety endpoint are:,

- All-cause death
- Any stroke
- Myocardial infarction
- Symptomatic valve thrombosis
- Pulmonary embolism
- Deep vein thrombosis
- Non-CNS systemic embolism
- Life-threatening or disabling bleeds (BARC type 3b, 3c or 5)
- Major bleeds (BARC type 3a).

The following details of NOAF are summarized by treatment:

- Subjects with NOAF reported on ECG but without medication switch
- Subjects with medication switch but without ECG evidence of NOAF
- Subjects with both ECG evidence and medication switch

Medication switch here means: requiring treatment with high dose oral anticoagulation as specified in 3.2.

Mean transaortic valve pressure gradient is measured by echocardiogram (TTE or TEE) at screening and at approximately 360 days after randomization. The difference between 360 days and screening is derived and analyzed exploratory by using a t-test.

The analysis the other variables are visualized in [flowchart 2](#) in appendix I.

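### For the cardiovascular-death composite and the primary bleeding endpoint, Kaplan-Meier cumulative risk with follow-up censored at death overstates the actual risk, because other deaths are competing events

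*Protocol*

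**What the plan says.** Four places have to be read together for the cardiovascular-death composite.

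- Protocol 10.3.6, on secondary and other efficacy variables: "The analysis methods are similar to those described for the primary efficacy variable".
- Protocol 10.3.5.1, which gives those methods: "Kaplan-Meier estimates of cumulative risk and cumulative hazard functions are provided to evaluate the timing of event occurrence". SAP 6.2.1.2 has the corresponding output: "Kaplan-Meier curves, one-sided log rank p-value, number of patients with event and incidence rate are provided".
- SAP 5.2.1, on the end of ITT follow-up: the efficacy cut-off date, the last known clinical status, "or date of death (by CEC adjudication) whichever comes first".
- Protocol 10.3.2, the first secondary endpoint: "the adjudicated composite of cardiovascular death, any stroke, myocardial infarction, symptomatic valve thrombosis" and the remaining thromboembolic events. SAP 6.2 adds that deaths of unknown cause count as cardiovascular: "The adjudicated composite of cardiovascular death (including unknown of unexplained death), any stroke".

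For the primary bleeding endpoint, Protocol 10.3.7 plans Kaplan-Meier cumulative risk directly and describes the analysis as descriptive, without formal tests. SAP 6.4.1.1 plans Kaplan-Meier curves for it under the same ITT scope.

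For single components, SAP 6.5 says that they "are analyzed exploratory and analogue to the superiority HR analysis as described in" SAP 6.2.1.2. Flowchart 2, which covers secondary and other variables, is not shown in the text available.

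Neither document mentions a cumulative incidence function, a Fine-Gray model or any other competing-risk method. Protocol 3.1 does recognise that competing events can preclude the event of interest in a frail population, and it answers by using all-cause mortality.

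**The concern.** Kaplan-Meier treats a censored subject as someone who could still have the event later. That is true of a subject who reaches the cut-off date, but not of one who has died. When deaths that are not part of the endpoint are censored, one minus Kaplan-Meier estimates the risk in a hypothetical world without those deaths, and it lies above the proportion of patients who actually have the event.

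The use of all-cause mortality removes the problem for the primary and net-clinical-benefit composites. It does not help the cardiovascular-death composite or the bleeding endpoint.

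Absolute risks are at stake. They matter most for bleeding, because the plan makes no formal bleeding test and the description is the main safety result. The distortion can also differ between arms if mortality differs.

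**Working it through.** **Planned figures.** HR = ln(1 − 0.264) / ln(1 − 0.33) = 0.7654. Schoenfeld events = 4 × (1.960 + 0.842)² / (ln 0.7654)² = 439.2, so 440. These match Protocol 10.4 and are not affected by this point. The documents give no planning figure for the cardiovascular-death composite.

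**Formulas** (constant cause-specific hazards). Let F be the risk of any first event including death, H = −ln(1 − F), and f the share of first events that are competing deaths.
- Actual risk (cumulative incidence) = (1 − f) × F
- One minus Kaplan-Meier = 1 − exp(−(1 − f) × H)

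**Cardiovascular-death composite, control arm.** F = 33.0% at 540 days (Protocol 10.4), so H = 0.4005. The documents do not give f, so I assume a range. The 11.5% row comes from the high-risk cohort in Protocol section 3: non-cardiovascular mortality of 24 − 14 = 10% at 1 year and 34 − 21 = 13% at 2 years, midpoint 11.5%.

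| Non-CV deaths as first event | f | Actual | 1 − KM | Excess (points) |
|---|---|---|---|---|
| 6% | 18% | 27.0% | 27.9% | 0.9 |
| 6.6% | 20% | 26.4% | 27.4% | 1.0 |
| 8% | 24% | 25.0% | 26.2% | 1.2 |
| 9.9% | 30% | 23.1% | 24.5% | 1.4 |
| 11.5% | 35% | 21.5% | 23.0% | 1.5 |
| 13.2% | 40% | 19.8% | 21.4% | 1.6 |

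At 720 days, F = 1 − exp(−0.4005 × 720/540) = 41.4%. The excess is then 1.7 points at f = 20% (34.8% against 33.1%) and 2.6 points at f = 40% (27.4% against 24.8%). A simulation of 400,000 subjects with f = 30% and censoring spread over 360 to 720 days gave 24.5% against 23.1% at 540 days, as in the table.

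**Bleeding endpoint.** The current text gives no bleeding rate, so only a relative size can be stated. For event risks of 1% to 12%, the excess is about 5–6% of the actual risk with 10% competing deaths, 12% with 20%, and 19–20% with 30%.

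**Stroke, if Kaplan-Meier curves are produced.** Protocol section 3 quotes stroke of 4.6% at 30 days, 6.0% at 1 year and 7.7% at 2 years, and death or stroke of 27% and 37% at 1 and 2 years.

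- *Strokes spread like deaths.* At 1 year: 1 − exp(−0.3147 × 0.06/0.27) = 6.75% against 6.0%. At 2 years: 1 − exp(−0.4620 × 0.077/0.37) = 9.2% against 7.7%. At 540 days, interpolating to 6.8% stroke and 31.8% death or stroke gives 7.9%, an excess of 1.1 points. With assumed inputs of 8% stroke and 28% death, 1 − exp(−0.4463 × 0.08/0.36) = 9.4%, an excess of 1.4 points.
- *Strokes early, as quoted.* Take both curves as linear between the quoted points. The stroke hazard added in each segment is (rise in stroke / rise in death or stroke) × ln(event-free at start / event-free at end). Death or stroke at day 30 is not given; I assume 4.6% to 10%. With 4.6%: 0.0471 + 0.0167 + 0.0116 = 0.0754, so 7.3%. With 10%: 0.0485 + 0.0172 + 0.0116 = 0.0773, so 7.4%. Against 6.8%, the excess is 0.4 to 0.6 points.

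**Unequal mortality (illustration).** With the same stroke hazard in both arms and an assumed death hazard ratio of 0.7654, the actual 2-year stroke risks are 7.7% and 8.0%, while one minus Kaplan-Meier is 9.2% in both.

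**The case against.** The case for leaving the plan alone has several parts.

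- *The inference is sound.* This stands in full. A reader might infer that the secondary tests are biased, but the log-rank test and the Cox model are valid comparisons of cause-specific hazards when other deaths are censored.
- *Component curves are not established.* This stands. A reader might infer that Kaplan-Meier risk is firmly planned for stroke, MI, PE and DVT. SAP 6.5 points to the hazard-ratio analysis, which in SAP 6.2.1.2 is the Cox model, and flowchart 2 cannot be read. Only the general sentence in Protocol 10.3.6 suggests it.
- *Risk differences are not planned.* This stands; neither document calls for them. SAP 6.2.1.2 offers the curves to show timing and consistency, and reports counts and incidence rates beside them. Protocol 10.3.5.1 and 10.3.7 nevertheless call the Kaplan-Meier output cumulative risk, and it will be read as such.
- *Competing risk was considered.* This is partly right. Protocol 3.1 raises it, so it cannot be said that the plan overlooked it, but the remedy does not reach the endpoints at issue here.
- *The size is modest.* This stands. The historical mortality comes from one high-risk cohort, whereas the trial requires an uncomplicated TAVR and excludes active malignancy and severe renal impairment. Some non-cardiovascular deaths follow a non-fatal event and so are not first events. Counting unknown deaths as cardiovascular reduces censoring further. The lower part of the table is therefore an upper-end case. Against this, the exclusion of periprocedural stroke may flatten the early stroke peak and move the stroke excess above its lower bound.

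**Conclusion.** The point holds for the cardiovascular-death composite and the primary bleeding endpoint. As written, the plan would report absolute risks that are somewhat too high. For the composite the excess is about 0.9 to 1.6 points at 540 days, assuming constant hazards, 33% primary events, and non-cardiovascular deaths making up about 18% to 40% of first events. The bleeding excess cannot be put in points because no current bleeding rate is given. For stroke it would be about 0.4 to 1.4 points at 540 days, conditional on curves being produced and on how early strokes occur. The historical rates are treated here as actual risks.

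The all-cause death component and the primary and net-clinical-benefit composites have no competing death and are unaffected. This is a worthwhile reporting improvement that changes no test result, hazard ratio, event count, incidence rate, type I error or power.

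**What to change.** In the SAP, for every endpoint that does not include all-cause death, replace one minus Kaplan-Meier with the Aalen-Johansen cumulative incidence, with non-event death as the competing event. For the cardiovascular-death composite that is non-cardiovascular death; for the bleeding endpoints it is any death that is not itself an endpoint event. Apply the same rule to single components if curves are shown for them, and state whether they will be. Keep the log-rank test and the cause-specific Cox hazard ratio.

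The cost is small. Deaths are already adjudicated and classified, so no new data are needed. The SAP code uses a two-level event status, so each affected endpoint needs one extra derived status variable. A short SAP amendment is also needed, with a check that the procedure is available in the SAS release used (SAP 4.1 allows 9.3 or higher).
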